A stroke occurs when a blood vessel that carries oxygen and nutrients to the brain is either blocked by a clot or bursts (or ruptures). When that happens, part of the brain cannot get the blood (and oxygen) it needs, so it and brain cells die. Stroke can be caused either by a clot obstructing the flow of blood to the brain (called an ischemic stroke) or by a blood vessel rupturing and preventing blood flow to the brain (called a hemorrhagic stroke). There are two types of hemorrhagic stroke: intracerebral hemorrhage (ICH) and subarachnoid hemorrhage (SAH). ICH stroke happens when a blood vessel inside the brain bursts and leaks blood into surrounding brain tissue. The bleeding causes brain cells to die and the affected part of the brain stops working correctly. SAH stroke involves bleeding in the area between the brain and the tissue covering the brain, known as the subarachnoid space. SAH stroke can be caused by malformation of the blood vessels, bleeding disorders, blood thinners, or most commonly by burst aneurysms. This type of stroke is called aneurysmal subarachnoid hemorrhage or aSAH.

Survivors of SAH often suffer from new depression disorders after recovery, resulting in a decreased quality of life and increased health care costs. Approximately 1/3 of all SAH patients without a previous history of mood disorder have signs or symptoms of depression at least one year after hospitalization. Multiple studies of patients who become depressed after any type of significant injury show that their treatment is at least twice the cost of patients who do not develop depression. This cost rises substantially with both age and depression severity.

Our goal with this study is twofold; first, to address the gap in knowledge of utility of prophylactic SSRI in the aSAH subpopulation of stroke patients, and second, to study the role of cortisol regulation in susceptibility to depression so that we might identify what patients would most benefit from SSRI prophylaxis. We hypothesize that placing aSAH patients on preventative anti-depressant medications at the time of stroke may both improve their lives and the lives of their families, while also decreasing post-injury health care costs.

Fluoxetine (an antidepressant commonly known as Prozac) is among a group of medications known as selective-serotonin reuptake inhibitors that work to maintain higher-than-normal levels of serotonin, a neurotransmitter popularly associated with contributions to well-being and happiness. Fluoxetine is a World Health Organization Essential Medicine and is considered a first-line treatment for depression by the American Psychiatric Association. In addition, fluoxetine has a fast treatment effects and is inexpensive. It is currently not standard to implement antidepressant medications after aneurysm rupture due to the lack of studies on their preventative benefits to aSAH patients.

The use of SSRIs has been studied in the general poststroke population, to include patients with aSAH. However, the aSAH population has not been evaluated as an independent experimental cohort. These studies demonstrated no difference in adverse events between the stroke population and general population. Furthermore, one arm of the ongoing poststroke depression triad trials (AFFINITY, FOCUS, and EFFECT) is also including aSAH patients, but again not looking at these patients as an independent experimental cohort. Meta-analyses have demonstrated "Poststroke depression has been shown in 6 double-blind controlled studies to be effectively treated with antidepressants, and 1 study has recently shown that PSD can be effectively prevented" (Robinson 2010). More granular studies evaluating SSRIs and hemorrhagic stroke also demonstrated adverse events to be no more frequent than controls as well as similar medical outcomes. Furthermore, in our current clinical practice, aSAH patients currently

on SSRIs at presentation are either continued on their SSRIs or restarted on their SSRIs following treatment, without increased clinical concern.

The University of Washington School of Medicine's Harborview Medical Center is the primary tertiary referral center for the Pacific Northwest and WWAMI region and a Certified Comprehensive Stroke Center, per the Joint Commission and American Heart Association/American Stroke Association. Each year over 200 patients are admitted to Harborview Medical Center for aneurysmal SAH. Harborview Medical Center maintains an Investigational Drug Service that manages medications used in clinical trials.

Eligibility criteria

- 1) Patients 18 years of age and older will be included.
- 2) Patients above 85 years of age will be excluded from the drug vs placebo cohort.
- 3) Patients admitted for subarachnoid hemorrhage from a ruptured cerebral aneurysm will be included.
- 4) Non-English speaking patients will be excluded.
- 5) Patients currently receiving therapy for depression or related mental health diagnoses before admission will be excluded.
- 6) Patients with medical contraindications to fluoxetine therapy will be excluded from the drug vs placebo arms
- 7) Pregnant patients or patients considering pregnancy during the trial period at the time of consent will be excluded from the drug vs placebo arms.
- 8) Patients with active psychosis will be excluded.
- 9) Patients who are incarcerated or in police custody will be excluded.
- 10) Patients with a comorbidity or cognitive impairment (as determined by a recruiter-administered Montreal Cognitive Assessment [MoCA]; Patients scoring >20 are considered of appropriate cognitive function for consent) that precludes informed

consent and participation in the research interviews will be excluded from the observational and drug vs placebo cohorts, but may be included in the biofluid cohort.

Who will take informed consent?

Potential patient-subjects will be identified by neurosurgeons on the treatment team. Patients will be recruited and screened for participation in the drug vs placebo or observational cohort by a member of the research team prior to discharge. Patient inclusion and exclusion will be determined by the medical record as well as in-person by the provider. The Montreal Cognitive Assessment will be administered prior to the consent to determine baseline cognitive state. We will also conduct screening to determine if the patient is currently receiving therapy for depression or related mental health diagnoses. Any recruiter who administers the MoCA completes MoCA training and certification. Patients scoring >20 on the MoCA are considered of appropriate cognitive function to participate in the study.

Patients recruited for the drug vs placebo cohort will be provided with a detailed explanation regarding the study protocol, occurrence of depression in aneurysmal subarachnoid hemorrhage and the potential treatment effects of fluoxetine. Patients will have an opportunity for questions before providing before consent. Decisional capacity will be determined by having participants confirm their understanding of the study purpose and procedure, and the risks, benefits and alternatives to participating in the study.

Interventions

Explanation for the choice of comparators

If a patient chooses to decline treatment with fluoxetine but is eligible for the observational cohort, they will be given the necessary study information. Patients can choose to provide consent anytime between approach and discharge. Patients may revoke their informed consent at any time by contacting the research team.

Intervention description

Patients deemed eligible for inclusion in the drugs vs. placebo or observational cohort will be approached for consent in the inpatient ward as they are nearing discharge after aSAH. After consent is obtained, patients will be randomized to either a placebo or fluoxetine-treatment group. Patients that decline participation in the drug vs placebo arm may be enrolled in the observational cohort.

For patients participating in the drug vs. placebo cohort, the study drug will be provided at no cost for the duration of the trial (1 year).

Patients randomized to the fluoxetine treatment group will be initially prescribed fluoxetine 20mg/day. The drug will be supplied to patients in 90-day supply. For patients in the drug/placebo cohort, if severe depression (as defined by a HAM-D score of >24 or a PHQ-9 score >20 or positive endorsement on the PHQ-9 suicide items 2 or 3) is persistent at any study time points, an additional fluoxetine dose of 20mg/day will be administered for 40mg total dose for fluoxetine group.

If severe depression is persistent at any study time points for patients randomized to the placebo group (as defined above), they will be prescribed 20 mg of fluoxetine.

The research assistant will administer an approximately 45-minute interview at up to five time points to all patient-subjects: upon enrollment (prior to hospital discharge) as a baseline assessment, and up to four follow-up visits within 18 months after discharge from the hospital.

The goal will be to do these assessments at the six-week, six-month, and one-year follow-up appointments, taking into consideration that the actual appointments frequently do not occur exactly on the intended timescale. The trial period will be for 12 months after discharge; however, should we need to speak with patients or if they miss their 12 month appointment, we will allow for another timepoint within 18 months.

The interview questionnaires will assess depression and health-related quality of life, medication compliance, drug side effects and pregnancy, either in person, over the phone, via email, or mail. If the participant endorses serious side effects, the event will immediately be reported to and reviewed by the study PI for its relatedness to the study and it will be reported to IRB in accordance with University of Washington IRB reportable event guidelines.

Depression will be assessed using the Hamilton Rating Scale for Depression (HAM-D) and the Patient Health Questionnaire (PHQ-9). Health-related quality of life will be assessed using the Medical Outcomes Short Form Health Survey (SF-36). All measures will be assessed at each time point.

For patients reaching the end of the study and choosing to discontinue the study drug, the two week weaning period will begin at the completion of the 12-month trial period. Patient education regarding continuation or discontinuation of SSRI treatment at the completion of the study will be provided 90 days prior to reaching the end of the study, regardless of treatment group. From time to time, members of the study team may contact the patient to ensure medication compliance and answer questions about medications and the study the subject may have.

If any patient, in the drug vs. placebo demonstrates severe depression (as defined by a HAM-D score of >24 or a PHQ-9 score >20 or positive endorsement on the PHQ-9 suicide items 2 or 3) is persistent at any study time points, patient will be immediately directed to their physician for further evaluation. If a patient endorses suicidal ideation, they will be immediately referred to the psychiatric service for further urgent mental health evaluation before a dosage increase is considered. If a patient is removed from the study, that data will be included in the subsequent data analysis.

After a final timepoint at approximately 1 year after hospitalization (but up to 18 months), the subjects' study enrollment will be complete.

Criteria for discontinuing or modifying allocated interventions

Patients may be withdrawn from the research without their consent if the patient is no longer able to participate in the research protocol. In any case that a patient-subject will be discontinuing the drug, we will taper over two weeks, halving the dose each week.

Outcome Measures

- For all subjects enrolled in the study, relevant clinical and demographic data, including PHI such as name, date of birth, dates related to hospital stay, medications, and medical record number.
- Montreal Cognitive Assessment (MoCA)- 30-item questionnaire to determine cognitive status.
- Patient Health Questionnaire 9 (PHQ9): 9-item questionnaire to treat and diagnosis depression.
- Hamilton Rating Scale for Depression (HAM-D: 30-item questionnaire to treat and diagnosis depression. This will be given if a patient exhibits depression based on the PHQ9 score.
- The Short Form (36) Health Survey (SF-36): 36-item questionnaire to assess health-related quality-of-life.
- Barthel Index: Scale used to determine functional status, measuring performance in activities of daily living.
- Hamilton Anxiety Rating Scale: Measures the severity of anxiety through looking at both psychic and somatic anxiety.
- Multidimensional Scale of Perceived Social Support: Scale to determine a patients social support system
- PROMIS: Sleep disturbance scale assess pure domain of sleep disturbance
- Health Care Utilization: Assess ER visits, outpatient visits, rehospitalization and mortality
- Fatigue Severity Scale: Measures the severity of fatigue and its effect on a person's activities and lifestyle in patients exhibiting depression

Participant timeline

The research assistant will administer an approximately 45-minute interview at up to five time points to all patient-subjects: upon enrollment (prior to hospital discharge) as a baseline assessment, and at up to four follow-up visits within 18 months after discharge from the hospital.

The goal will be to do these assessments at the six-week, six-month, and one-year follow-up appointments, taking into consideration that the actual appointments frequently do not occur exactly on the intended timescale. The trial period will be for 12 months after discharge; however, should we need to speak with patients or if they miss their 12 month appointment, we will allow for another timepoint within 18 months.

For patients reaching the end of the study and choosing to discontinue the study drug, the two week weaning period will begin at the completion of the 12-month trial period. Patient education regarding continuation or discontinuation of SSRI treatment at the completion of the study will be provided 90 days prior to reaching the end of the study, regardless of treatment group. From time to time, members of the study team may contact the patient to ensure medication compliance and answer questions about medications and the study the subject may have.

Sample size

Based upon previous studies we anticipate the rate of depression in the treatment group to be 7.3% and the rate of depression in the placebo group to be 21.2%, as determined by the HAM-D score. It is estimated that 200 patients are eligible per year, however we have conservatively estimated enrolling 20 patients to account for recruitment and retention rates. Power calculations show a large-scale trial would require 224 total patients. We anticipate analysis at 1-year (as funded from this proposal) will demonstrate the feasibility of both the randomized administration of antidepressant medication to the post-SAH population, as well as prospectively define the rate of new depression and the effect of SAH on health-related quality of life.

Recruitment

Patients will be recruited and screened for participation by a member of the research team prior to discharge. Patient inclusion and exclusion will be determined by the medical record as well as in-person by the provider. The Montreal Cognitive Assessment will be administered prior to the consent to determine baseline cognitive state. We will also conduct screening to determine if the patient is currently receiving therapy for depression or related mental health diagnoses. Any recruiter who administers the MoCA completes MoCA training and certification. Patients scoring >20 on the MoCA are considered of appropriate cognitive function to participate in the study.

Patients recruited for the drug vs placebo cohort will be provided with a detailed explanation regarding the study protocol, occurrence of depression in aneurysmal subarachnoid hemorrhage and the potential treatment effects of fluoxetine. Patients will have an opportunity for questions before providing before consent. Decisional capacity will be determined by having participants confirm their understanding of the study purpose and procedure, and the risks, benefits and alternatives to participating in the study.

Relevant clinical and demographic data such as name, date of birth, dates related to hospital stay, medical record number, area of the ruptured aneurysm, Glasgow Coma Score, Fisher Grade, Hunt and Hess Grade, Medications, medical history, and comorbidity which will be maintained in a secure screening and recruitment log. Patients can choose to provide consent anytime between approach and discharge. Patients may revoke their informed consent at any time by contacting the research team.

Assignment of interventions: allocation

Sequence generation

Simple randomization schemes will be utilized for the drug cohort and placebo cohort. For each cohort, subjects will be randomized in a 1 to 1 ratio to receive either the SSRI antidepressant or placebo drugs. Randomization will be done after the participant or

LAR as signed the ICF. Randomization will be performed by the study pharmacist. Study team, study assessor, study investigator is blinded until the subject exits the study, need to unblind for medical intervention, or end of the study.

Assignment of interventions: Blinding

Who will be blinded

Trial participants, care providers, outcome assessors will stay blinded. Placebo vs study drug will be prepared and dispensed by local study pharmacist. Only the study pharmacy will know the designation of each participant until the clinical team request the information for health care purposes or when the participants exit the study.

Procedure for unblinding if needed

If an adverse event occurs in which the disclosure of the treatment arm is necessary for medical treatment, the disclosure will be provided to the patient and/or provider.

Data collection and management

Plans for assessment and collection of outcomes

Preventative treatment of poststroke depression in aneurysmal subarachnoid hemorrhage					
Activity	Initial Screening	Baseline	6-week	6-month	12-month
Eligibility Screen	x				
Montreal Cognitive Assessment (MoCA)*	x				
Enrollment	x				
Consent	x				
OnCore/EPIC Update	x	x	x	x	x
Pharmacy Prescription Fluoxetine (every 90 days)		x	x	x	
Patient Health Questionnaire (PHQ-9)		x	x	x	x

Hamilton Rating Scale for Depression (HAM-D)**		x	x	x	x
36-Item Short Form Survey (SF-36)		x	x	x	x
Barthel Index		x	x	x	x
Hamilton Anxiety Rating Scale (HAM-A)		x	x	x	x
Multidimensional Scale of Perceived Social Support		x	x	x	x
Sleep Disturbance (PROMIS)		x	x	x	x
Self Report Health Service Utilization and Medication Use		x	x	x	x
Fatigue Severity Scale (FSS)		x	x	x	x
Disclosure of Interventional Cohort					x
*MoCA score must score more than 20 in order to be enrolled and consented into the study					
**HAM-D only conducted when pt scores greater than 4 on PHQ-9					

Confidentiality and Data management

All research data will be deidentified. A single-master key will be retained. All data will be stored on a secure research database or in a secure cabinet on a secure floor.

Access to identifiers will be limited to the study team. Data will be classified as Level 4 risk. U1-U13, D1-D9 will apply to all data. S1-S20 will be utilized; local procedures will be utilized in addition to the protections afforded by utilizing the UW OneDrive. P1-P3 will be utilized for non-digital records. T1-T8 will be utilized for data transmission. We do not intend to utilize vendors, but if vendors are utilized we will adhere to V1.

Statistical methods

Statistical methods for primary and secondary outcomes

In addition to patient-level measures, relevant clinical and demographic data will be

obtained for the descriptive statistics of the cohort. For each time point we will determine the rate and severity of the outcome measures. We will utilize linear mixed models to determine to determine the treatment effect of preventative fluoxetine administration in patients surviving subarachnoid hemorrhage. Important confounders will be determined and adjusted for in the analysis. The primary outcome will be analyzed at the one-year time point. The intermediate time points will be obtained to determine the longitudinal progression of the mental health status and functional ability in this patient population.

Oversight and monitoring

Composition of the coordinating centre and trial steering committee

The PI (or approved co-investigator) will monitor the study with prompt reporting of adverse events and other study related information to the IRB and other agencies as appropriate. Non-serious adverse events and unrelated serious adverse events will be reported in the annual progress report. Serious adverse events that could be related to the study should be reported within 7 days of becoming aware of the event. At any time, if a patient presents suicidal ideations, the patient will be immediately referred to psychiatric service for further evaluation and the event reported. Team meetings by the PI and staff will be conducted on a routine basis to discuss any new adverse events or changes in the protocol. This plan will be revised and updated if the benefit-risk analysis changes.

Composition of the data monitoring committee, its role and reporting structure

An independent medical monitor, an appropriately qualified physician with no conflict of interest and meeting the NINDS recommendation of being otherwise unaffiliated with the study or an institution conducting the study, will perform safety-focused reviews considering adverse events at a minimum of 6 month intervals.

Adverse event reporting and harms

The PI (or approved co-investigator) will monitor the study with prompt reporting of adverse events and other study related information to the IRB and other agencies as

appropriate. Non-serious adverse events and unrelated serious adverse events will be reported in the annual progress report. Serious adverse events that could be related to the study should be reported within 7 days of becoming aware of the event. At any time, if a patient presents suicidal ideations, the patient will be immediately referred to psychiatric service for further evaluation and the event reported.

If an adverse event occurs in which the disclosure of the treatment arm is necessary for medical treatment, the disclosure will be provided to the patient and/or provider.

Frequency and plans for auditing trial conduct

Internal audit will be conducted routinely with study PI and the study team. An independent medical monitor, an appropriately qualified physician with no conflict of interest and meeting the NINDS recommendation of being otherwise unaffiliated with the study or an institution conducting the study, will perform safety-focused reviews considering adverse events at a minimum of 6 month intervals.

Plans for communicating important protocol amendments to relevant parties (e.g. trial participants, ethical committees)

Team meetings by the PI and staff will be conducted on a routine basis to discuss any new adverse events or changes in the protocol. This plan will be revised and updated if the benefit-risk analysis changes.

Dissemination plans

A description of this clinical trial will be available on <https://clinicaltrials.gov>, as required by U.S. Law. This Web site will not include information that can identify you. At most, the Web site will include a summary of the results. You can search this Web site at any time.

Patient Health Questionnaire Depression (PHQ-9) (Kroenke et al., 2001)

For this next section, the questions I'll be asking you will be in regards to your mood in the past month, since your injury.

Phq	Since your injury, how often have you been bothered by any of the following problems?	Not at all	A little of the time	More than half the time	Nearly all the time
1.	Little interest or pleasure in doing things	0	1	2	3
2.	Feeling down, depressed or hopeless	0	1	2	3
3.	Trouble falling or staying asleep, or sleeping too much	0	1	2	3
4.	Feeling tired or having little energy	0	1	2	3
5.	Poor appetite or overeating	0	1	2	3
6.	Feeling bad about yourself- or that you are a failure or have let yourself or your family down	0	1	2	3
7.	Trouble concentrating on things, such as reading the newspaper or watching television	0	1	2	3
8.	Moving or speaking so slowly that other people could have noticed? Or the opposite - being so fidgety or restless that you have been moving around a lot more than usual	0	1	2	3
9.	Thoughts that you would be better off dead or of hurting yourself in some way. *Note, if any endorsement, RA assess further and contact PI [9a.] Do you currently have plans to harm yourself or take your own life? Yes No if no, proceed to next section [9b.] Have you attempted to carry out this plan in the past two weeks? Yes No	0	1	2	3
10.	[If YES to any problems] How difficult have these problems made it for you to do your work, take care of things at home, or get along with other people?	0 Not at all	1 A little bit	2 Moderately	3 Extremely

Total Score: _____

The Hamilton Rating Scale for Depression

1. DEPRESSED MOOD (Sadness, hopeless, helpless, worthless)

- 0=** Absent
- 1=** These feeling states indicated only on questioning
- 2=** These feeling states spontaneously reported verbally
- 3=** Communicates feeling states non-verbally—i.e., through facial expression, posture, voice, and tendency to weep
- 4=** Patient reports VIRTUALLY ONLY these feeling states in his spontaneous verbal and non-verbal communication

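### Rescue for persistent severe depression is written separately for each arm, with no procedure for ordering, dispensing or explaining it under the blind

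*Combined protocol and SAP*

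**What the plan says.** All references are to the combined protocol and SAP.

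**Rescue (Intervention description).** The trigger is severe depression that persists at a study time point, "as defined by a HAM-D score of >24 or a PHQ-9 score >20 or positive endorsement on the PHQ-9 suicide items 2 or 3". The action is then stated by arm. On fluoxetine, "an additional fluoxetine dose of 20mg/day will be administered for 40mg total dose for fluoxetine group". On placebo, the protocol says that "for patients randomized to the placebo group (as defined above), they will be prescribed 20 mg of fluoxetine". Later in the same section, patients who meet the trigger are sent to their physician. Those with suicidal ideation are to be "referred to the psychiatric service for further urgent mental health evaluation before a dosage increase is considered".

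**Blinding.** Under Who will be blinded: "Trial participants, care providers, outcome assessors will stay blinded". The study pharmacist prepares and dispenses both products.

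**Release of the code.** Three places give three conditions:

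- Sequence generation: "Study team, study assessor, study investigator is blinded until the subject exits the study", with further exceptions for a medical intervention that needs unblinding and for the end of the study.
- Who will be blinded: "Only the study pharmacy will know the designation of each participant until the clinical team request the information for health care purposes", or until the participant leaves the study.
- Procedure for unblinding if needed: an adverse event whose treatment requires knowledge of the arm, in which case "the disclosure will be provided to the patient and/or provider".

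The schedule of activities plans disclosure of the arm only at the 12-month visit.

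**The concern.** A clinician who follows the rescue text literally must know the arm to know which of the two instructions applies. A patient on placebo who is told that fluoxetine is now being prescribed can infer the original allocation. So can the research assistant: the same interview that collects the depression and quality-of-life scores also asks about medication compliance and side effects, and the schedule lists a self-report form covering medication use at each visit.

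The depression, anxiety and quality-of-life outcomes (PHQ-9, HAM-D, HAM-A, SF-36) are self-reported or rated by an interviewer, so knowledge of the arm can shift later scores. The disclosure would not be random. It is set off by a bad depression score, and if fluoxetine works as the protocol expects, it would probably occur more often on placebo. This is a bias in measurement. How to analyse one-year data from placebo patients who have started fluoxetine is a separate question, which masking would not settle.

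**Working it through.** **1. What each instruction adds.** Taking the placebo-arm amount as daily, as the protocol does for fluoxetine elsewhere:

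- fluoxetine arm: 40 − 20 = 20 mg added;
- placebo arm: 20 − 0 = 20 mg added.

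The increments are equal, so a single order to add a step would carry out both instructions. The protocol does not say that this is how rescue is done. It also does not say who orders rescue, whether the added drug is masked, whether the placebo continues, what the patient is told, or whether the interviewer stays blind afterwards.

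**2. Do the code-release conditions cover rescue?** The adverse-event procedure does not mention it. The medical-intervention exception and the health-care-purposes wording are both broad enough for a routine rescue to release the code. Nothing rules that out.

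**3. Timing.** Follow-up is at six weeks, six months and one year, and the primary outcome is analysed at one year (Statistical methods). Rescue triggered at the first two visits precedes that analysis. Rescue triggered at the 12-month visit cannot affect that visit's scores.

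**4. The plan's own sample size.** Sample size gives HAM-D depression rates of 21.2% (placebo) and 7.3% (fluoxetine) and 224 patients for a large-scale trial. Alpha and power are not stated. With 1:1 allocation and an assumed two-sided 5% test at 85% power, without continuity correction:

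n per arm = [1.960 × √(2 × 0.1425 × 0.8575) + 1.036 × √(0.212 × 0.788 + 0.073 × 0.927)]² / 0.139² = 112.0, so 2 × 112 = 224.

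An assumed 80% power with continuity correction gives 113 per arm, 226 in total, which is also close. The figure serves here only to scale the counts to 112 per arm.

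**5. How many rescues?** The planned enrolment is 20; 10 per arm is assumed.

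- Depressed on placebo: 10 × 0.212 = 2.12. On fluoxetine: 10 × 0.073 = 0.73. Total 2.85.
- At 112 per arm: 23.7 + 8.2 = 31.9.
- Share of depressed patients who are on placebo: 0.212 / (0.212 + 0.073) = 74%.

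Rescue needs severe, persistent depression, and the documents do not give that share. Let f be the assumed share of depressed patients who qualify, the same in both arms. Expected rescues are 2.85 × f among 20 and 31.9 × f among 224. With independent patients, the chance of at least one rescue among 20 is 1 − (1 − 0.212f)¹⁰ × (1 − 0.073f)¹⁰.

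| f (assumed) | Expected rescues of 20 | Chance of at least one of 20 | Expected rescues of 224 |
|---|---|---|---|
| 10% | 0.29 | 25% | 3.2 |
| 25% | 0.71 | 52% | 8.0 |
| 50% | 1.43 | 78% | 16.0 |
| 100% | 2.85 | 96% | 31.9 |

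These counts cover all visits. The documents do not allow a split into the visits before one year, which are the ones that matter.

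**The case against.** The strongest reply is that the documents describe a blind that could survive rescue. The added amount is the same in both arms, the pharmacy alone holds the code and dispenses, and the suicidal-ideation sentence speaks only of a dosage increase without naming an arm. A reader might infer from the arm-specific wording that rescue cannot be ordered without revealing the arm, or that the blind fails. The documents support neither. Masked delivery is compatible with every sentence in them, and none says that the clinician or patient is told the arm in order to rescue. That part of the reply stands.

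It is also fair to say that the 20-patient study is presented mainly as a feasibility exercise, that few rescues are expected in it, and that releasing the code for medical need is an ordinary safety provision.

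The gap remains all the same. Being able to mask rescue is not the same as a written procedure for doing so. The text that staff will follow names a different action for each arm, and two of the three release conditions would let the code out for it. A study meant to show that randomised administration is feasible should also show a workable blind.

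**Conclusion.** The concern holds as a procedural gap with a real route to bias: arm-specific rescue instructions, no masked way to carry them out, and code-release conditions that disagree and do not mention rescue. The arm can become known at six weeks or six months, before the one-year analysis.

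Its size cannot be fixed from the documents. The range is about 0.3 to 2.9 expected rescues among 20 patients, assuming 10 per arm and a qualifying share of 10% to 100% that is equal across arms. The top of that range is a ceiling only if every rescued patient is also a HAM-D case. Endorsing a suicide item alone can trigger rescue, so this is not guaranteed.

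Two further inferences should be avoided:

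- From 21.2% v 7.3% a reader might infer that unblinding would fall about 3:1 on placebo (0.212 / 0.073 = 2.9). That ratio is for any depression. The ratio among severe, persistent cases could be higher or lower. An excess on placebo is likely, but its size is unknown.
- A reader might take the rescued patients to be those who carry the primary endpoint. The documents give no HAM-D cut-off for that endpoint, and the severe cases are only a subset of the depressed patients.

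**What to change.** Leave the drug content of each arm's rescue as the Intervention description states it, and specify its delivery.

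1. The blinded clinician writes one arm-neutral order for a study-medication step. The study pharmacist, who already holds the code and prepares both products, fills it with the same number of identical-looking, identically labelled units and the same instructions in both arms. The patient and research assistant are told only that the study medication has been stepped.
2. If medical care does require the arm, keep it from the outcome interviewer, and say in the protocol how this is done.
3. Reconcile the Intervention description with Sequence generation, Who will be blinded and Procedure for unblinding if needed, so that they agree on when the code is released, to whom, and how rescue relates to that. Which release rule applies is for the sponsor and the clinical team; this review does not choose one.

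The cost is protocol wording, one pharmacy order form and some additional matched units. The drawback is that patients learn of a step without learning its content, so the consent form needs a sentence to say so.
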